### **Procedures to be included from protocol 1 (See protocol 1 for complete description of these procedures)**

Pulmonary function, depression and apathy, Reflex and voluntary cough procedures, Swallowing evaluation procedures will be completed in a manner identical to that described in the preceding paragraphs.

### **Procedures unique to protocol 2:**

Longitudinal measurement of swallowing and cough function: Measures of swallowing and cough will be collected at 3 time points spaced 10 – 18 months apart.

For participants who were also in study protocol 1, those swallowing and cough data will be used for the first time-point in order to reduce participant burden.

Longitudinal measures of Participant disease status: Disease severity (unified Parkinson's disease rating scale and Hoehn & Yahr score), medications, levodopa equivalent dose, and surgical status (specifically deep brain surgery) will be recorded at each study visit.

Pharmacologic and/or surgical therapies for PD may have known and unknown influences on swallowing and/or cough function (i.e., (43)) and will therefore be recorded for this study.

Swallow and cough outcome measures (described in detail in protocol 1):

1. Slope of UtC sensitivity
2. Cough sensitivity: Capsaicin concentration that elicits the 2-cough response (C2)
3. Cough motor (airflow) measures: CPD, PEFR, PEFRT, CVA
4. Swallowing performance measures: Penetration-aspiration scale scores (PAS)
5. Swallowing physiology measures: SRT, dtLVC\_H1, dtLVC\_B1, dLVC, PTT

**Statistical analysis:** In the statistical analysis, we would fit a linear mixed effects model to take into account the repeated measurement by regarding each subject as a cluster. Specifically, in the analysis, the repeatedly measured outcome, i.e. change of penetration-aspiration scale scores (PAS), C2, cough and swallowing physiology variables from baseline, will be fitted by adjusting for fixed effects terms including baseline PAS, age, sex, medications, levodopa equivalent dose, surgical status, and disease duration (2=third 10-18 month; 1=second 10-18 month; and 0=first 10-18 month) and the random effects term due to participants. Restricted resampling model selection (Zou et al. 2015) technique will be adopted to conduct the valid statistical inference for repeated measurement data and it is also robust to missing data which is particularly useful for this study. **Expected outcomes:** Results of this aim are expected to provide a clinical deliverable in the form of sensitive and specific predictor(s) of airway protection dysfunction that are more customized for patients with different PD durations. As well, because of the study's prospective longitudinal design, this study will also be the first to examine the natural history of cough function in people with PD over the proposed 3-year time period.

**Data storage:** All participant records will be maintained in HIPPA compliant storage. Paper copies of the ICF will be kept in a locked cabinet, in the locked research laboratory of the PI (D2-063 or DG-143; [name]). Paper data collection forms will be kept in a separate, locked file cabinet, also in the research laboratory of the PI. Paper forms will not include participant names or dates; rather participants will be assigned a unique participant ID number that will be kept separate from the name. Electronic database files containing summary data for individual participants and compiled data for all participants will be saved according to participant number within a limited access, password protected folder on the PI's P-drive.

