## **5. Specific Aims:**

The specific aims for this project are:

Aim 1: To determine the relationships between blunted airway somatosensation, reflex cough sensitivity and effectiveness, and swallowing function in people with PD.

Hypothesis 1: We predict that blunted airway somatosensation will appear earlier (years 0 – 5 post-diagnosis) in the disease process than either cough or swallowing dysfunction, and that by 6-10 years post-diagnosis, blunted respiratory somatosensation will correlate with reduced reflexive cough sensitivity and effectiveness, and decline in swallow function and safety.

Specific aim 2: To determine whether measures of discriminative and affective processing of general airway sensation is/are associated with deficits in reflex cough and swallowing function in people with PD.

Hypothesis 2: People with PD will exhibit reduced discriminative processing components of airway stimuli. With disease progression, measures of affective processing components will decline and this will directly correlate with diminished reflex cough sensitivity and swallowing function.

Specific aim 3: To determine whether over-filtering of airway stimuli is associated with swallowing or cough deficits in people with PD.

Hypothesis 3: Over-filtering of airway stimuli will be associated with deficits in reflex cough and swallowing function in people with PD.

Aim 4: Determine the relationships between observable motor aspects of swallowing, cough, and cough sensitivity over a 3-year time period in people with PD.

Hypothesis 4: Swallowing safety and physiology in people with PD will exhibit significant differences over 3 time points, spaced 10 – 18 months apart. For people within 9 years of PD diagnosis, reduced reflex cough sensitivity will not be a sensitive and/or specific indicator of swallowing dysfunction. However, for those with a greater disease duration (10+ years), reflex cough sensitivity will be a sensitive and specific biomarker of swallowing dysfunction.

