### **Protocol 2 (aim 4)**

**Participants:** This study will include men and women with PD, and we will recruit from those participating in protocol 1, in addition to the general PD population at UF Fixel Institute for Neurological diseases given protocol 2's larger required N. For participants who did complete protocol 1, the procedures will not be replicated in protocol 2 (therefore these participants would only complete the 2nd and 3rd protocol 2 visits). The inclusionary and exclusionary criteria will be identical to those of protocol 1, with the exception that this protocol will also include people with possible or probable progressive supranuclear palsy (PSP) or multiple systems atrophy (MSA).

**Power Analysis:** To test the hypothesis that the relationship between swallow and cough motor deficits, and reflex cough sensitivity varies as a function of disease duration in PD, we would compare the penetration/aspiration scale change from baseline with 10 to 18 months apart for PD patients. As shown in our pilot study data, the mean (SD) penetration-aspiration scale change from baseline for the first two 10 to 14 months period are 2.08 (1.97) and 2.82 (2.33), respectively. Based on it, to reach a 0.85 power by controlling the type I error rate to 0.05 for detecting this effect size with two-sided test, we would need 155 PD patients.

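### Protocol 2 follows each participant for 20 to 36 months, with three years as the maximum, and its mixed model records time only as a coarse 0/1/2 period code

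*Combined protocol and SAP*

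**What the plan says.** - **Visit spacing.** Hypothesis 4 (5. Specific Aims) predicts that swallowing "will exhibit significant differences over 3 time points, spaced 10 – 18 months apart". The section Procedures unique to protocol 2 sets the same schedule: "Measures of swallowing and cough will be collected at 3 time points spaced 10 – 18 months apart".
- **Stated span.** Aim 4 concerns swallowing, cough and "cough sensitivity over a 3-year time period in people with PD". The expected outcomes of Protocol 2 promise the "natural history of cough function in people with PD over the proposed 3-year time period".
- **Planning figures.** The Power Analysis proposes to "compare the penetration/aspiration scale change from baseline with 10 to 18 months apart for PD patients", but its inputs come from a narrower window: the mean (SD) "scale change from baseline for the first two 10 to 14 months period are 2.08 (1.97) and 2.82 (2.33").
- **Model.** The Protocol 2 statistical analysis fits a linear mixed model to change from baseline. Its only time term is called disease duration and takes the values 0, 1 and 2 for the first, second and third 10-18 month period. No term for elapsed months is listed.
- **Participants from Protocol 1.** "For participants who did complete protocol 1, the procedures will not be replicated in protocol 2"; their Protocol 1 data serve as the first time point.

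**The concern.** Aim 4 is a natural-history aim, so the quantity of interest is change per unit of time. The schedule allows an eight-month window at the second visit and a sixteen-month window at the third, and the model cannot see where in the window a participant was measured. Two people progressing at the same rate can contribute different changes to the same category. The estimated change per period then depends partly on when visits happened to be booked, and it has no fixed meaning in months.

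Three wording problems sit on top of this. A reader of the aim would expect three years of follow-up, which most schedules within the window do not reach. The planning changes come from 10 to 14 month periods, while the study permits 10 to 18, and nothing explains the difference. The period code lists three periods where the visit schedule supplies two. In addition, the code carries the label disease duration, which Hypothesis 4 uses for years since diagnosis (within 9 years, or 10 and more).

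**Working it through.** **1. The plan's own figure.** Inputs from the Power Analysis: changes 2.08 (SD 1.97) and 2.82 (SD 2.33), two-sided alpha 0.05, power 0.85, N = 155.
- Contrast: 2.82 − 2.08 = 0.74.
- SD of the difference with zero correlation between the two changes (the plan gives no correlation): √(1.97² + 2.33²) = √9.3098 = 3.051.
- Normal approximation: n = [(1.960 + 1.036) × 3.051 / 0.74]² = 152.6, so 153. A paired t-test gives exactly 155.

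The stated size reproduces from the 10 to 14 month inputs.

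**2. Span.** Three time points give two gaps.
- Minimum 2 × 10 = 20 months, maximum 2 × 18 = 36, midpoint 28.
- Second visit: months 10 to 18. Third visit: months 20 to 36.
- Ratio of longest to shortest elapsed time at either visit: 18/10 = 36/20 = 1.8.

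**3. How well the code tracks time.** The windows do not overlap (18 is less than 20), so order is kept. Assume each gap is uniform over 10 to 18 months and independent of the other. Each gap then has variance 8²/12 = 5.33. Elapsed time has mean 14 and variance 5.33 at the second visit, and mean 28 and variance 10.67 at the third. Average within-visit variance is 8 and between-visit variance is (14/2)² = 49. The correlation of code with elapsed months is √(49/57) = 0.93.

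**4. Size in PAS points.** Assume that pilot periods last 12 months and that 2.82 is cumulative from baseline.
- First-period rate: 2.08/12 = 0.173 per month. Second-period rate: 0.74/12 = 0.062 per month.
- Expected change at month 10: 10 × 2.08/12 = 1.73.
- Expected change at month 18: 2.08 + 6 × 0.74/12 = 2.45.
- Spread across the second-visit window: 2.45 − 1.73 = 0.72, beside the planned contrast of 0.74.

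If the first-period rate continued unchanged, month 18 would give 18 × 2.08/12 = 3.12 and a spread of 1.39.

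**5. Effect on sample size.** Keep the contrast at 0.74 and add the variance due to timing, with uniform gaps as in step 3.
- First-period rate in the first gap and second-period rate in the second: added variances 0.160 and 0.181, total 9.651. n = 152.6 × 9.651/9.310 = 158.2, so 159.
- Constant rate 2.82/24 = 0.1175: added variances 0.074 and 0.147, total 9.531. n = 156.3, so 157.

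Against 153 this is about 3 to 4% more. If instead the 0.74 contrast scaled in proportion to the gap from a 12-month reference, the required n would be 220 at 10 months, 153 at 12, 113 at 14 and 68 at 18.

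**6. Number of periods.** Three time points yield two changes from baseline. Three full periods would need four time points and 3 × 10 = 30 to 3 × 18 = 54 months. The code fits the visit schedule only if 0 denotes the baseline visit, where change is zero by definition, and the text does not say that.

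**The case against.** The strongest reply is that the defect is mild and several harsher readings fail. Most of this stands.

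- A reader might infer that the three-year claim is contradicted. It is not: 36 months lies inside the permitted range and is its upper end.
- A reader might infer that visit number is not a valid measure of time. The windows are disjoint and the code is correctly ordered, so it is coarse rather than invalid.
- A reader might infer that scheduling alone moves the second-visit change by more than the planned effect, by setting 1.39 against 0.74. That needs the first-period rate to run on to month 18, although the pilot figures slow after the first period. With the slower rate the spread is 0.72. It is also a range between window extremes, whereas 0.74 is a difference in means, so it measures spread and not bias.
- A reader might infer that participants carried over from Protocol 1 can have a first gap above 18 months. The spacing rule and the carry-over rule stand next to each other, and the spacing can be read as covering the carried-over visit. No exemption is stated.
- A reader might infer that sicker participants attend later, which would confound time with severity. Nothing in the documents shows this, and the model adjusts for baseline PAS, medications, levodopa equivalent dose and surgical status.
- A reader might infer that 155 is too few. The figure reproduces, and the wider window only extends upward from the same 10-month floor.

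The reply does not remove the missing elapsed-time term, the unexplained change of window or the mismatch in the number of periods.

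**Conclusion.** The point holds in a limited form. Follow-up is 20 to 36 months, and three years is reached only when both gaps are at their limit. The time code is ordered but coarse, with up to a 1.8-fold difference in elapsed months at the same visit, so the change per period is partly a product of scheduling. On the pilot rates the expected second-visit change varies from 1.73 to 2.45 PAS points across the window. That rests on 12-month pilot periods, on 2.82 being cumulative, and on the slower rate applying after month 12. The plan confirms none of these.

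The consequence is for interpretation of a natural-history estimate. Sample size is barely affected (about 3 to 4%), and no bias has been demonstrated. The conflict between three coded periods and two available changes is independent of these assumptions and needs resolving whichever time variable is used. The change is worth making because it is cheap.

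**What to change.** 1. In the Protocol 2 statistical analysis, model time as actual months since each participant's own baseline assessment, taking the Protocol 1 assessment as baseline for carried-over participants. Use a flexible form, or keep the visit factor and add each participant's deviation from the nominal visit time. A single straight line would not suit pilot rates that fall from 0.173 to 0.062 per month.
2. Report estimated change at 12 and 24 months. Both fall inside the visit windows.
3. Give this term its own name and keep it separate from years since diagnosis.
4. Reconcile the three coded periods with the three time points, and say what code 0 means if any code is kept.
5. If three time points are confirmed, replace the three-year wording in Aim 4 and in the expected outcomes with 20 to 36 months.
6. In the Power Analysis, state that the planning changes come from 10 to 14 month intervals and why they are taken to apply to 10 to 18.

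**Cost.** Wording and one model term, with no new visits, participants or procedures. The stated follow-up becomes less favourable. The Data storage section says that paper forms carry no dates, so elapsed months must be recorded in the analysis dataset and cannot be assumed to be recoverable from the forms.

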***Reflex Cough Assessment Procedures:***

Participants will be outfitted with a facemask covering the nose and mouth. The facemask will be coupled to a pneumotachograph, differential pressure transducer, and have a side port with a one-way inspiratory valve for nebulizer connection. The nebulizer will be connected to a dosimeter that delivers aerosolized solution during inspiration with a delivery duration of 2 seconds. The cough airflow signal will be digitized (Power Lab Data Acquisition System) and recorded (LabChart 7; ADInstruments, Inc.) to a laptop computer.

Participants will be seated for an initial 30 seconds of quiet breathing in order to acclimate to the facemask. Participants will then complete a capsaicin challenge with three randomized blocks of

0, 50, 100, 200, and 500  $\mu$ M capsaicin dissolved in a vehicle solution. Participants will be given the instruction “cough if you need to” prior to capsaicin delivery. The solution will be administered automatically upon detection of an inspired breath and there will be a minimum of one minute between each trial. Participants will be provided water to drink between trials. Following each capsaicin trial, participants will rate their urge-to-cough on a modified Borg Rating Scale measured 0-10, where 0 is no urge, and 10 is maximal urge. Our research group has extensive experience utilizing this methodology to induce cough (e.g., (1, 34-36)). We also hold an FDA IND # 76866 for the use of capsaicin in the study of cough reflex sensitivity and motor pattern.

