***Voluntary cough procedure:***

Voluntary cough will be assessed using the same equipment used for reflex cough testing, without the nebulizer attached to the side port (side port is capped off). The participant will be asked to produce a sequential voluntary cough three times into the facemask attached to the pneumotachograph, and to maintain a comfortable seated position for all cough testing. Each cough trial will be separated by approximately 1 minute of quiet breathing. Participants will be given the following instructions for cough production: “When you are ready, cough as if something has gone down the wrong pipe.”

**Cough outcome variable:** The concentration of capsaicin that elicits the 2-cough response (C2) will be recorded and serve as our measure of cough reflex sensitivity. Additionally, airflow measurements will be derived from the reflex and voluntary cough waveforms. Measurements will include compression phase duration (CPD), peak expiratory flow rate (PEFR), and peak expiratory flow rise time (PEFRT) and cough volume acceleration (CVA=PEFR / PEFRT).

**Urge-to-cough (UtC):** Following each capsaicin trial participants will rate their urge-to-cough (UtC) on a modified Borg rating scale, where 0 is no UtC, and 10 is maximal UtC. The UtC provides information regarding participants’ perceived magnitude of the stimulus.

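### Aim 4 fits a linear model to change in C2, but C2 is known only within limits set by the 50 to 500 µM ladder, so the estimated change depends on an unstated code for patients without a 2-cough response

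*Combined protocol and SAP*

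**What the plan says.** All references are to the combined protocol and SAP.

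- **Reflex Cough Assessment Procedures.** Participants "complete a capsaicin challenge with three randomized blocks of" "0, 50, 100, 200, and 500" µM, and are instructed "cough if you need to". A cough is therefore not forced, and nothing above 500 µM is tested.
- **Cough outcome variable** (under Voluntary cough procedure). "The concentration of capsaicin that elicits the 2-cough response (C2) will be recorded and serve as our measure of cough reflex sensitivity".
- **Protocol 2.** The cough test is repeated in the same way at three time points, and C2 is the second listed swallow and cough outcome.
- **Protocol 2, Statistical analysis.** A linear mixed effects model is fitted in which "the repeatedly measured outcome, i.e. change of penetration-aspiration scale scores (PAS), C2, cough and swallowing physiology variables from baseline, will be fitted". The scale for C2 is not stated. The only text on incomplete data is about the model selection technique: "it is also robust to missing data which is particularly useful for this study".
- **Protocol 2, Expected outcomes.** The plan says "this study will also be the first to examine the natural history of cough function in people with PD" over the proposed three years.
- **Protocol 1, Statistical Analysis, Aims 2 and 3.** Cough outcomes also enter regressions there, again with no coding rule for C2.

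No section assigns a C2 to a participant with no 2-cough response by 500 µM, and none says how three blocks are reduced to one C2.

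**The concern.** C2 is a threshold observed in intervals: at or below 50, between 50 and 100, between 100 and 200, between 200 and 500, or above 500 µM. A linear model of change needs one number at each end. A patient above 500 µM at both visits has an unknown change, but any fixed code turns it into exactly zero and dropping removes the patient. A patient who moves from 500 µM to no response contributes whatever the code says.

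The missing-data sentence does not close the gap. It describes a property of model selection. A C2 above 500 µM is not missing at random: it is unobserved because it is high, and dropping such patients removes the least sensitive ones.

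At stake is the size of C2 progression, part of the natural history that the plan promises to describe. If reflex sensitivity declines over time, as the study's premise suggests, the non-response share rises between visits, and that is when the choice of code changes the answer.

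**Working it through.** **The plan's own figure.** The documents give no figure for C2. The only sample-size figure is 155, based on change in the penetration-aspiration scale (PAS) (Protocol 2, Power Analysis). The difference is 2.82 − 2.08 = 0.74, and with zero correlation the SD of the difference is √(1.97² + 2.33²) = 3.05. A paired t-test at two-sided 0.05 with power 0.85 needs 154.6, so 155. It reproduces, and C2 plays no part in it.

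**Step 1: arithmetic with assumed shares.** Shares at 50/100/200/500/no response are assumed to be 20/20/20/20/20% at baseline and 15/15/20/20/30% at follow-up. With code c for no response:
- baseline mean = 0.20 × (50 + 100 + 200 + 500) + 0.20c = 170 + 0.20c
- follow-up mean = 7.5 + 15 + 40 + 100 + 0.30c = 162.5 + 0.30c
- change = 0.10c − 7.5, which is 42.5 µM (c = 500), 92.5 (c = 1000) or 192.5 (c = 2000)

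In general, a net share p moving from 500 µM to no response adds p × (c − 500) µM. If the share is constant and nobody is dropped, the code has no effect on the mean change.

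**Step 2: the ceiling alone, log2 scale.** Assumptions, none from the documents: normal log2 threshold with SD 1.5, visit correlation 0.6, and true first-to-third change 0.50. The baseline mean is log2(500) − 1.5 × z(1−p) for baseline non-response p. Simulated mean change, with thresholds at or below 500 µM treated as exactly known:

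| Baseline non-response | 2% | 5% | 10% | 20% | 40% |
|---|---|---|---|---|---|
| Dropped | 0.47 | 0.45 | 0.42 | 0.38 | 0.33 |
| Coded 500 | 0.48 | 0.46 | 0.43 | 0.38 | 0.27 |
| Coded 1000 | 0.51 | 0.51 | 0.50 | 0.48 | 0.40 |
| Coded 2000 | 0.53 | 0.55 | 0.58 | 0.59 | 0.53 |

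Check at 10%: third-visit non-response is Φ(−1.28 + 0.50/1.5) = 17%. Each doubling of the code adds 0.17 − 0.10 = 0.07, which takes 0.43 to 0.50 and then to 0.58 (unrounded steps).

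**Step 3: adding the 50 µM floor and the coarse grid.** This uses the planned type of model (change at visits 2 and 3, visit as factor, random intercept, covariates not simulated):

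| Baseline non-response | 2% | 5% | 10% | 20% | 40% |
|---|---|---|---|---|---|
| Dropped | 0.35 | 0.38 | 0.38 | 0.36 | 0.31 |
| Coded 500 | 0.36 | 0.38 | 0.36 | 0.30 | 0.19 |
| Coded 1000 | 0.38 | 0.42 | 0.44 | 0.41 | 0.32 |
| Coded 2000 | 0.40 | 0.47 | 0.51 | 0.52 | 0.45 |

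At 2 to 5% most of the shortfall for dropping or code 500 comes from the floor and grid, because 44% and 28% of baseline thresholds lie at or below 50 µM. Code 2000 looks unbiased at 10 to 20% only because the upward error from the code cancels the downward error from the floor and grid. Dropping leaves about 121 of 155 usable third-visit changes at 10% and 97 at 20%.

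**Step 4: untransformed µM.** At 10% the estimated change is 54 (dropped or coded 500), 90 (coded 1000) or 162 (coded 2000), a three-fold spread from the same data.

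**Step 5: the alternative.** An interval-censored random-intercept model gave 0.50 at 10, 20 and 40%, with 95% interval coverage 0.94/0.96/0.94. Power was 0.99/0.99/0.97, against 0.96/0.94/0.80 for code 500 and 0.98/0.98/0.96 for code 2000.

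**The case against.** The strongest reply is that every magnitude is assumed. The documents give no rate of capsaicin non-response, no SD, no visit correlation and no shift. The Background describes silent aspiration, which is not failure to cough at 500 µM. If everyone responds by 500 µM at every visit, the ceiling problem disappears. This stands: non-response is plausible here, but its frequency is unknown.

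Three stronger readings are tempting and should not be drawn.

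- A reader might infer that every modest code pulls progression toward zero. It does not. With the ceiling alone, code 1000 is close to unbiased up to about 10% non-response and understates only above that. Its lower values in Step 3 at those rates come from the floor and grid.
- A reader might compare the µM estimates with a true µM change. Any such value rests mostly on an assumed tail above 500 µM that the study never observes. Only the spread between codes is safe to report.
- A reader might infer that Aim 4 as a whole is compromised. C2 is one of many outcomes, and the plan ties no decision to a C2 effect size. Detection also changes less than the size of the estimate.

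It can also be said that a censored model asks for more than the defect strictly requires, since a log scale with one fixed code and a sensitivity analysis would remove the analyst's freedom. That is fair as a minimum. It would not remove the bias from the floor and grid.

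**Conclusion.** The concern holds and is worth correcting before analysis, though it does not threaten the trial. That the estimated C2 change depends on an unstated code follows from the text, provided some patients do not reach two coughs at 500 µM and their share changes, or they are dropped. Under the Step 2 assumptions, dropping or coding 500 understates progression at every rate examined, code 1000 does so above about 10%, and code 2000 overstates it. At 10% the four choices run from 0.42 to 0.58 against a true 0.50. The floor and grid lower all of them further.

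Not affected are the sample size of 155, the urge-to-cough slope (it needs no 2-cough response), and a Hypothesis 4 classification with a cut-off at or below 500 µM, provided non-responders are kept as test-positive.

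**What to change.** 1. Record no 2-cough response at 500 µM as >500 µM and keep these patients in the analysis.
2. In Protocol 2, Statistical analysis, replace the linear model of change for C2 with a model of C2 at all visits on the log scale: an interval/right-censored mixed model, or an ordinal mixed model. Add a random-slope version as a sensitivity analysis.
3. Use the same coding where C2 enters the Protocol 1 regressions.
4. State in the same text, before analysis, how one C2 is derived from the three blocks. One example is the lowest concentration giving at least two coughs in at least two of the three blocks.
5. If a linear model is kept, the minimum is the log scale, one code for >500 µM fixed before analysis, and a sensitivity analysis over other codes.

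Other outcomes and covariates stay as planned. The cost is SAP wording and one data code, with no new data or visits. There are downsides. The estimate is less familiar than a mean difference in µM, and the resampling model selection may need a separate run for C2. The censored model also assumes a distribution for the log threshold. With heavy-tailed or skewed thresholds it gave 0.47 to 0.52 (coverage 0.91 to 0.97). With unmodelled patient slopes (SD 0.3 log2 per visit) it gave 0.50/0.47/0.44 with coverage 0.97/0.94/0.88 at 10/20/40% non-response, which is why the random-slope check is included.

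### The Aim 4 model names baseline PAS as the only baseline outcome covariate, so changes in C2, cough airflow and swallow timing have no own-baseline term specified

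*Combined protocol and SAP*

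**What the plan says.** The Statistical analysis paragraph under Protocol 2 (aim 4) sets out one linear mixed model, with a participant random effect, for "the repeatedly measured outcome, i.e. change of penetration-aspiration scale scores (PAS), C2, cough and swallowing physiology variables from baseline". It gives a single covariate list for all of these outcomes: they "will be fitted by adjusting for fixed effects terms including baseline PAS, age, sex, medications, levodopa equivalent dose, surgical status", plus a period term labelled disease duration. Baseline PAS is the only baseline outcome value in the list. Nothing says that it is swapped for the matching baseline when the outcome is not PAS.

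The outcome list under Procedures unique to protocol 2 includes C2, "Cough motor (airflow) measures: CPD, PEFR, PEFRT, CVA", and the swallow-timing measures SRT, dtLVC_H1, dtLVC_B1, dLVC and PTT. On timing, it says: "Measures of swallowing and cough will be collected at 3 time points spaced 10 – 18 months apart". Each outcome's own baseline is therefore in hand. Participants who completed Protocol 1 supply it from that protocol.

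The same paragraph applies a resampling-based model selection. It does not say which terms must stay in the model.

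**The concern.** The authors chose to analyse change adjusted for baseline, and for PAS change the covariate fits that choice. For every other outcome the adjustment uses another variable's starting value. A change score is negatively correlated with its own starting value, and baseline PAS can absorb only the small part of that variation which it shares with the outcome's baseline. The rest stays in the residual and widens the intervals for between-person coefficients such as age, sex, treatment and surgical status. Aim 4 asks how swallowing, cough and cough sensitivity relate to one another, and the plan expects predictors from it, so between-person precision matters.

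There are two further stakes. If people who leave the study differ at baseline on the outcome concerned, a model without that baseline does not use the information that explains their leaving. And because the covariate list is open and terms may be selected, whether own baseline enters could be decided after the data are seen.

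**Working it through.** **The plan's own figure.** The Power Analysis gives PAS changes "for the first two 10 to 14 months period are 2.08 (1.97) and 2.82 (2.33), respectively", aims "to reach a 0.85 power by controlling the type I error rate to 0.05 for detecting this effect size with two-sided test", and concludes "we would need 155 PD patients". The difference is 2.82 − 2.08 = 0.74. If the two changes are uncorrelated, the SD of their difference is √(1.97² + 2.33²) = √9.3098 = 3.051. The normal approximation gives n = (1.960 + 1.036)² × 9.3098 / 0.74² = 152.6, and the paired t calculation gives 154.6, so 155. The figure reproduces. It rests on PAS, whose own baseline is already in the model, so this point does not alter it.

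**Assumptions for the rest.** The documents give no visit-to-visit correlation (ρ) and no correlation between baseline PAS and another outcome's baseline (r). I take ρ = 0.5 to 0.8 and r = 0.2 to 0.4, equal SDs at each visit, and a link between baseline PAS and the change that runs only through the outcome's baseline. C2 takes few distinct values, so for C2 the results are approximate.

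**Precision, one change score.** Share of change variance explained:
- by own baseline: (1 − ρ)/2, which is 25% at ρ = 0.5 and 10% at ρ = 0.8;
- by baseline PAS: r²(1 − ρ)/2, which runs from 0.04 × 0.10 = 0.4% to 0.16 × 0.25 = 4%.

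The ratio of residual variances, PAS-adjusted over own-baseline-adjusted, is [1 − r²(1 − ρ)/2] / [(1 + ρ)/2]:

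| ρ | r | Ratio |
|---|---|---|
| 0.5 | 0.2 | 0.990 / 0.75 = 1.32 |
| 0.5 | 0.4 | 0.960 / 0.75 = 1.28 |
| 0.8 | 0.2 | 0.996 / 0.90 = 1.11 |
| 0.8 | 0.4 | 0.984 / 0.90 = 1.09 |

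Own baseline is therefore worth 9% to 32% more patients for between-person coefficients.

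**Two changes per person.** Three visits give two changes. With equal correlation between all visits, the mean of the two changes has variance 1.5(1 − ρ) without own baseline and (1 + ρ)/2 − ρ² with it, in units of the outcome variance. At ρ = 0.5 these are 0.75 and 0.50, so the SE ratio is √(0.50/0.75) = 0.816, a fall of about 18%. Simulation with 155 patients (4,000 runs per setting) gave falls of about 27%, 17%, 9% and 3% at ρ = 0.3, 0.5, 0.7 and 0.9. The single-change figures are thus not inflated, and the gain becomes small when ρ is high.

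**Period contrast.** With complete data, own baseline is constant within a person and drops out of the comparison between periods. At ρ = 0.5 the simulated SE was 0.0881 with and without it. When dropout was made to depend on own baseline, the stated model biased the period contrast by about 0.07 to 0.09 SD, against 0.01 to 0.02 SD with own baseline. Those sizes depend on the assumed dropout and correlation pattern. The direction is the useful result. Milder dropout or higher ρ gives less bias, and if correlation fades with time, own baseline reduces the bias without removing it.

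**The case against.** The covariate list opens with the word *including*, so it does not rule out own-baseline terms. A reader might infer that the other outcomes are never adjusted for their own baseline. The text supports only that the adjustment is not specified. PAS, the primary swallowing outcome and the only powered one, already has its own baseline. Hypothesis 4 begins with differences over three time points, and with complete data that contrast is untouched. All of this stands and limits the point to the non-PAS outcomes.

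The stronger reading is that the stated model creates false regression-to-the-mean associations. Simulation can be made to show this. Take 155 patients and a covariate correlated 0.3 with own baseline that has no effect on follow-up *given observed baseline*. The stated adjustment then rejects in 40%, 36%, 28% and 20% of runs at ρ = 0.5, 0.6, 0.7 and 0.8, against about 5% with own baseline. That definition of no effect makes the own-baseline model correct by construction.

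Suppose instead that the covariate tracks the true stable level (correlation 0.3) and has no effect on change. The result reverses. The model without own baseline rejects in about 5% of runs, and the own-baseline model in 47%, 47%, 36% and 17% at ρ = 0.3, 0.5, 0.7 and 0.9. This is Lord's paradox. Age, sex, drug dose and surgery are not randomised here, and the two models answer different questions: change overall, or change among people with equal baselines. The documents do not settle which pattern holds, so the general claim is not supported.

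A narrower case is plausible. Baseline PAS and the swallow timings come from the same fluoroscopic study and may share measurement error. With an assumed error correlation of 0.3, a false baseline-PAS association appeared in about 87% of runs. Adding own baseline lowered this to 26%, 49%, 69% and 82% at ρ = 0.3, 0.5, 0.7 and 0.9. It was reduced, not removed.

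**Conclusion.** The gap is real and limited. One covariate list serves all change outcomes, and its only baseline outcome value matches PAS alone. For C2, cough airflow and swallow timing, specifying own baseline would be worth about 9% to 32% more patients for between-person coefficients at the assumed correlations, and less if ρ exceeds 0.8. It also gives some protection to the period contrast if dropout depends on baseline level. It does not change that contrast with complete data, and it does not change the 155.

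Confidence is high on what the text says and moderate on the size, which rests on correlations that the documents do not give. The plan should not be read as generally producing regression-to-the-mean findings, because that depends on how a covariate relates to the true and the measured baseline. This is a cheap improvement.

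**What to change.** In the Protocol 2 Statistical analysis paragraph, replace *baseline PAS* in the covariate list with *the baseline value of the outcome being modelled*. Baseline PAS may stay as an extra covariate for non-PAS outcomes. State that the own-baseline term is always retained and is not subject to model selection.

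Add one sensitivity analysis for the between-person coefficients: either the same model without own baseline, or a joint model of the raw values at all three visits. Say in advance that a coefficient which differs materially between the two will be reported as dependent on the choice of adjustment.

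The cost is one changed phrase, two or three added sentences and one extra model per outcome. No new patients, visits or measurements are needed. The downside is the one named above: in a non-randomised cohort, adjusting for an error-prone baseline can create associations for covariates that track the true starting level. The sensitivity analysis is there to expose them.
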